5.12 Withdrawal of individual subjects

Subjects can leave the study at any time for any reason if they wish to do so without any consequences. The investigator can decide to withdraw a subject from the study for urgent medical reasons.

5.12.1 Specific criteria for withdrawal (if applicable)

n.a.

5.13 Replacement of individual subjects after withdrawal

If test subjects lose weight, other test subjects will be approached, so that there are at least 10 participants in the (pilot) study

5.14 Follow-up of subjects withdrawn from treatment

subjects will be followed-up after withdrawal if medically required.

5.15 Premature termination of the study

n.a.

6. SAFETY REPORTING

6.1 Section 10 WMO event

In accordance to section 10, subsection 1, of the WMO, the investigator will inform the subjects and the reviewing accredited METC if anything occurs, on the basis of which it appears that the disadvantages of participation may be significantly greater than was foreseen in the research proposal. The study will be suspended pending further review by the accredited METC, except insofar as suspension would jeopardise the subjects' health. The investigator will take care that all subjects are kept informed.

6.2 AEs, SAEs and SUSARs

6.2.1 Adverse events (AEs)

Adverse events are defined as any undesirable experience occurring to a subject during the study, whether or not considered related to [the investigational product / the experimental intervention]. All adverse events reported spontaneously by the subject or observed by the investigator or his staff will be recorded.

6.2.2 Serious adverse events (SAEs)

A serious adverse event is any untoward medical occurrence or effect that at any dose:

- results in death;
- is life threatening (at the time of the event);
- requires hospitalisation or prolongation of existing inpatients' hospitalisation;
- results in persistent or significant disability or incapacity;
- is a congenital anomaly or birth defect;
- Any other important medical event that may not result in death, be life threatening, or require hospitalization, may be considered a serious adverse experience when, based upon appropriate medical judgement, the event may jeopardize the subject or may require an intervention to prevent one of the outcomes listed above.

The sponsor will report the SAEs through the web portal *ToetsingOnline* to the accredited METC that approved the protocol, within 15 days after the sponsor has first knowledge of the serious adverse events.

SAEs that result in death or are life threatening should be reported expedited. The expedited reporting will occur not later than 7 days after the responsible investigator has first knowledge of the adverse event. This is for a preliminary report with another 8 days for completion of the report.

6.2.3 Suspected unexpected serious adverse reactions (SUSARs)

n.a.

6.3 Annual safety report

n.a.

6.4 Follow-up of adverse events

All AEs will be followed until they have abated, or until a stable situation has been reached. Depending on the event, follow up may require additional tests or medical procedures as indicated, and/or referral to the general physician or a medical specialist. SAEs need to be reported till end of study within the Netherlands, as defined in the protocol.

6.5 [Data Safety Monitoring Board (DSMB) / Safety Committee]

n.a.

7. STATISTICAL ANALYSIS

7.1 Primary study parameter(s)

-corelation coefficients between stimulus strength and AFI signal amplitude will be calculated. The statistical significance of the correlation will be calculated using linear regression analysis.

-repeated-measures ANOVAs will be performed between baseline recordings and recordings 1 hour after application of lidocaine/prilocaine cream and between baseline recordings and recordings 1 week after application of a capsaicin patch. Finally, a paired t-test will be used to compare 1.0mA, 5Hz and 1.0mA, 2000Hz electrical stimulation.

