Figure 2: high density of nociceptor endings in the epidermis, demonstrated by immunohistochemical staining with PGP9.5. The endings have a somewhat "variceus" aspect. In these thickenings there is a high concentration of mitochondria (see figure 3).

Figure 3: electron microscopic recording of an axon terminal (A) and Schwann cell (SC) of a nociceptor termination. The arrow shows 11 mitochondria in this ending.

Figure 4: sharp decrease in the number of epidermal nociceptor endings in an animal model for neuropathy. sham = control animal, CCI = animal with chronic constriction injury (model

for neuropathy), u.dermis is upper dermis. The arrowheads show PGP9.5 labeled epidermal nociceptor endings, which are completely absent in the epidermis in the animal with neuropathy.

OBJECTIVES

Primary Objective:

To study whether painful neuropathy can be measured with flavoprotein imaging, first of all a pilot study is needed, with which we want to investigate whether a reproducible and validated flavoprotein signal can be obtained at the second fingertip of healthy subjects.

STUDY DESIGN

- studying whether there is a time relationship between administering an electrical stimulus by means of finger electrodes and an optical (flavoprotein) signal on the fingertip of test subjects
- studying whether there is a linear relationship between the strength of the applied electrical signal and the size of the optical (flavoprotein) signal
- studying whether the signal is specific to the flavoprotein wavelength, by changing the filter settings of the camera
- studying whether the optical (flavoprotein) signal can be blocked by administering lidocaine / prilocaine cream on the fingertip
- studying whether the optical (flavoprotein) signal can be blocked by administering a capsaicin 8% patch on the fingertip.

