2.4 Sample size calculation

AFI of the fingertip is a completely new application, there are no data on the basis of which a sample-size calculation can be done. It is a pilot study. The results of this pilot will serve to calculate a sample size for a follow-up study.

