5.9 Study parameters/endpoints

5.9.1 Main study parameter/endpoint

- magnitude and time course of the flavoprotein response
- linearity of the electrical stimulation with the flavoprotein response
- block of the flavoprotein response by lidocaine / prilocaine cream and 8% capsaicin patches

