5.11 Study procedures

- 1) Each subject will undergo a series of electrical stimuli (5Hz, for 10 seconds) with AFI measurement. Each stimulus strength (0.5, 0.6, 0.7, 0.8, 0.9 and 1.0 mA) will be administered twice. The stimulus is interrupted when the pain intensity exceeds 7. Thereafter, a (non-painful) 2000Hz, 1.0mA stimulus will be administered as a (negative) control for 10 seconds. The stimuli are administered by a Neurometer, a validated before (11). The middle finger is illuminated with a white light source, from which blue light with a wavelength of 480nm is filtered. This light excites oxidized flavoproteins. The signal is picked up by a digital camera that is connected to an upright microsoop. The stimulation and measurements take 15 minutes.

- 2) At the end of the above measurements, the middle finger tip is smeared with lidocaine / prilocaine cream. An hour later the test person returns for the same measurements described above (15 minutes).
- 3) At the end of the measurements described under 2) an 8% capsaicin patch is applied to the middle finger tip. After an hour the researcher comes along and the plaster is removed. A week later the test person returns to undergo the measurements as described under 1) again (15 minutes).

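### Linearity is a main endpoint, but the only analysis named for it tests for a zero slope, which cannot tell a linear response from many threshold or saturating ones

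*Protocol*

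**What the plan says.** The Study design section lists as an aim "studying whether there is a linear relationship between the strength of the applied electrical signal and the size of the optical (flavoprotein) signal", and the Summary repeats it. Section 5.9.1 makes "linearity of the electrical stimulation with the flavoprotein response" one of three main endpoints.

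For this endpoint section 7.1 states that "corelation coefficients between stimulus strength and AFI signal amplitude will be calculated" and then: "The statistical significance of the correlation will be calculated using linear regression analysis". No criterion for r is given. No curvature term, lack-of-fit test or alternative model is named.

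The other analyses in 7.1 have other targets. One part reads "repeated-measures ANOVAs will be performed between baseline recordings and recordings 1 hour after application of lidocaine/prilocaine cream", with a parallel comparison for the capsaicin patch; these address the block. The last is that "a paired t-test will be used to compare 1.0mA, 5Hz and 1.0mA, 2000Hz electrical stimulation", which addresses the negative control. Sections 7.2 and 7.3 are marked not applicable.

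On the data, section 5.11 says: "Each stimulus strength (0.5, 0.6, 0.7, 0.8, 0.9 and 1.0 mA) will be administered twice". Section 2.4 says that "there are no data on the basis of which a sample-size calculation can be done".

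**The concern.** Testing a Pearson correlation and testing the slope of a simple linear regression are the same test, with a zero slope as the null. Rejecting it shows that the response changes with stimulus strength. The straight line is assumed by the model and is not examined by the test. A response that is absent below a threshold, all-or-none, or flat after an early rise can give a clearly significant slope.

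Section 7.1 does not say that a significant correlation will be read as linearity, but it names nothing else that could answer the endpoint. The report would have only r and p to go on, and a threshold or saturating signal could be described as linear.

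**Working it through.** **Inputs.** Six strengths, 0.5 to 1.0 mA, each given twice (section 5.11); 10 subjects (section 2.2). The protocol states no variance, alpha or power, so there is no figure to reproduce. Assumed: two-sided alpha 0.05; residual SD of 0.3, 0.5 or 1.0 of the full response; between-subject SDs of gain and level of 0.3 each; the response shapes below.

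**Step 1: noise-free correlation.** The centred strengths are ±0.05, ±0.15 and ±0.25, so Sxx = 2 × (0.0025 + 0.0225 + 0.0625) = 0.175. With r = Sxy / √(Sxx × Syy):

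| Shape (response at 0.5, …, 1.0 mA) | Sxy | Syy | r |
|---|---|---|---|
| Linear (0, 0.2, 0.4, 0.6, 0.8, 1) | 0.350 | 0.700 | 1.00 |
| Threshold above 0.7 mA (0, 0, 0, 1/3, 2/3, 1) | 0.367 | 0.889 | 0.93 |
| Mid-range step (0, 0, 0, 1, 1, 1) | 0.450 | 1.500 | 0.88 |
| Plateau (0, 0.6, 0.9, 1, 1, 1) | 0.315 | 0.795 | 0.84 |
| Step at the top (0, 0, 0, 0, 0, 1) | 0.250 | 0.833 | 0.65 |

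The last row shows that not every rising curve gives a high r. Many do.

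**Step 2: the planned test with noise.** Simulation of 5,000 trials per cell, duplicates averaged, pooled regression on 10 × 6 = 60 points. Lack of fit compares strength as a six-level factor with a linear term, allowing for subject: F on 4 and 45 df. Entries are for SD 0.3 / 0.5 / 1.0.

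| Shape | Slope significant (%) | Median pooled r | Lack of fit significant (%) |
|---|---|---|---|
| Linear | 100 / 100 / 93 | 0.66 / 0.58 / 0.41 | 2.5 / 3.4 / 4.6 |
| Threshold | 100 / 100 / 95 | 0.67 / 0.59 / 0.42 | 93 / 56 / 17 |
| Mid-range step | 100 / 100 / 99 | 0.68 / 0.63 / 0.48 | 100 / 96 / 46 |
| Plateau | 100 / 99.9 / 84 | 0.56 / 0.50 / 0.36 | 99.8 / 88 / 31 |

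Taking r per subject (12 recordings) does not help. It is significant in 86 / 56 / 20% of subjects for linear data, against 85 / 56 / 21% (threshold), 90 / 66 / 27% (step) and 73 / 42 / 16% (plateau).

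**Step 3: a different error structure.** With 10 × 6 × 2 = 120 independent observations and no between-subject variation, the slope test at SD 1.0 rejects in 96% of runs for linear data, 97% for the same threshold, 99.7% for the step and 93% for a plateau reached at 0.7 mA. In that setting a quadratic term alone detects the mid-range step in only 1–4% of runs, because the step is symmetric about the centre. The factor comparison is the more general check.

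**Step 4: what the deviations would show.** The largest true deviation from the fitted line is:

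- Step, at 0.7 mA: slope 0.450/0.175 = 2.571, fitted 0.5 − 0.05 × 2.571 = 0.37, true 0, deviation 0.37.
- Plateau, at 0.5 mA: slope 0.315/0.175 = 1.8, fitted 0.75 − 0.25 × 1.8 = 0.30, true 0, deviation 0.30.
- Threshold, at 0.7 mA: slope 0.367/0.175 = 2.095, fitted 0.333 − 0.05 × 2.095 = 0.23, true 0, deviation 0.23.

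The mean 95% CI half-width for such a deviation is 0.12 / 0.20 / 0.40. The intervals are informative at SD 0.3. At SD 1.0 they would show that the shape is undetermined.

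**The case against.** The strongest objection is that model checks and rules of interpretation commonly go in a SAP, which is not at hand, and that 7.1 never says a significant r establishes linearity. The second part is true. However, 7.1 is not silent here: it assigns a specific method to a main endpoint, and that method tests a different hypothesis.

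A second objection is that linearity may be meant loosely, as a graded association, and that no later step of the protocol depends on strict linearity. The wording of 5.9.1 and of the design aim does not support the loose reading. The lack of a dependent decision does limit the consequence.

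A third is that r itself carries information on fit, and that its failure to separate the shapes comes from the assumed between-subject SDs. With those set to zero, pooled r is the noise-free r × √(V / (V + SD²/2)), where V = Syy/6. At SD 0.3 this gives 0.85 linear, 0.81 step, 0.81 threshold and 0.73 plateau. At SD 0.5 it gives 0.69 linear and 0.72 step. The reversal at SD 0.3 in the table does depend on the assumption, but separation remains weak, and no cut-off for r is stated.

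A fourth stands as a caveat. Section 5.11 interrupts a stimulus when pain intensity exceeds 7, so the upper strengths may be incomplete. If only five strengths were usable in every subject, lack-of-fit power would be 87 / 46 / 14% for the threshold and 98 / 70 / 23% for the plateau. With four strengths it would be 61 / 26 / 10% and 79 / 38 / 14%. A subject-level model can use incomplete data, so the check remains possible with less power.

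**Conclusion.** The concern holds. The analysis named for the linearity endpoint shows whether the response changes with stimulus strength and does not by itself establish that the relation is linear. This follows from the null hypothesis of the test and needs no assumption about noise. The simulated rates do rest on assumed shapes, SDs, alpha and complete data. Over that range a significant result is about as likely under a mid-range step or a threshold as under a straight line, and somewhat less likely under a plateau when noise is high.

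This should be fixed before analysis. It affects one of three main endpoints, but the study is a 10-subject pilot and no stated decision turns on strict linearity.

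**What to change.** In section 7.1:

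- Keep the slope, described as evidence of a stimulus-related response.
- Within the subject-level model, add the comparison of strength as a six-level factor against a linear term (4 df).
- Report the mean response at each strength and the deviations from the fitted line, with 95% CIs.
- State that a significant slope alone does not support a claim of linearity, and that significant lack of fit counts against it.
- State that non-significant lack of fit is not proof of linearity and must be read with the CIs. If these still include large deviations, the conclusion is that the response is stimulus-related and its shape not determined.
- State how recordings from interrupted stimuli enter this comparison.

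The cost is one further model comparison on recordings already planned, a few sentences in 7.1, and a more cautious conclusion if the data are noisy. No further stimulation, visits or subjects are needed.

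### Linearity of the stimulus-response relation is a main endpoint, but section 7.1 tests only for a trend, which a clearly non-linear rising response would also pass

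*Protocol*

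**What the plan says.** The Protocol's Study design section lists as an aim "studying whether there is a linear relationship between the strength of the applied electrical signal and the size of the optical (flavoprotein) signal". Section 5.9.1 repeats it as one of three main endpoints: "linearity of the electrical stimulation with the flavoprotein response".

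Section 7.1 gives this endpoint two statements: "corelation coefficients between stimulus strength and AFI signal amplitude will be calculated", and "The statistical significance of the correlation will be calculated using linear regression analysis". It names no curvature or lack-of-fit test and does not say how subject enters the regression.

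The other comparisons in section 7.1 do get within-subject methods: "repeated-measures ANOVAs will be performed between baseline recordings" for the two blocking interventions, and "a paired t-test will be used to compare 1.0mA, 5Hz and 1.0mA, 2000Hz electrical stimulation" for stimulus frequency.

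On the data, section 5.11 says "Each stimulus strength (0.5, 0.6, 0.7, 0.8, 0.9 and 1.0 mA) will be administered twice". Section 2.2 gives 10 volunteers. Section 2.4 says there is no basis for a sample size calculation and that the pilot will be used to size a follow-up study.

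**The concern.** A correlation, or the slope behind it, tests the hypothesis of no linear trend. Rejecting it says that signal and stimulus move together. It does not separate a straight line from a response that saturates, or from one that is absent below a threshold and constant above it. Followed as written, the plan could report a main endpoint as met when the data contradict it.

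A smaller point sits in the same sentence. Each subject contributes 12 baseline recordings, and the stated method leaves open whether recordings or subjects are the unit. The error rate of the trend test depends on that choice. The follow-up study also needs a mean slope and its between-subject spread, and a pooled fit does not supply the spread.

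**Working it through.** **Inputs from the Protocol.** 10 subjects; 6 strengths x 2 = 12 recordings per subject per session; 10 x 12 = 120 at baseline. The plan has no power or sample size figure to reproduce.

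**Assumptions.** Residual SD = 1; two-sided alpha 0.05; L = between-subject SD of level; C = between-subject SD of the change over 0.5-1.0 mA. Simulations used 20,000 trials per setting.

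**1. How straight a non-linear curve looks.** Code the strengths -5, -3, -1, 1, 3, 5 (sum of squares 70).
- Plateau, rising 2 SD by 0.7 mA: responses 0, 1, 2, 2, 2, 2. Sxy = 13, Syy = 3.5, r = 13/sqrt(70 x 3.5) = 0.83.
- Midway step of 2 SD: 0, 0, 0, 2, 2, 2. Sxy = 18, Syy = 6, r = 18/sqrt(70 x 6) = 0.88.

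**2. What the slope test does with the plateau.** The fitted rise over the range is 10 x 13/70 = 1.86 SD. With strength scaled to run from -0.5 to 0.5, each subject's sum of squares is 2 x 70/100 = 1.4, so the fitted rise of one subject has sampling variance 1/1.4 = 0.714. The SE of the mean of 10 is sqrt((0.714 + C^2)/10).
- C = 0: SE 0.267, ratio 1.86/0.267 = 7.0.
- C = 1: SE 0.414, ratio 1.86/0.414 = 4.5.

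Both far exceed the 9-df critical value of 2.26. In simulation with L 1-2 and C up to 1, the slope is significant in 93-100% of trials (pooled or subject-slope test). The 2 SD step is significant in nearly all.

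**3. What a test of linearity does with the same data.** Take each subject's six strength means, remove that subject's fitted line, and test the mean deviations. That leaves 6 - 2 = 4 df for the mean deviation and 10 x 4 - 4 = 36 df for the subject-by-strength residual. The noncentrality is 20 x (Syy - Sxy^2/70), where 20 is the number of recordings per strength:
- Plateau: 20 x (3.5 - 2.414) = 21.7; detected in about 95% of simulated trials.
- Step: 20 x (6 - 4.629) = 27.4; detected in about 99%.
- Truly linear response: about 5% false alarms.

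One quadratic coefficient per subject, tested over the 10 subjects, detects the plateau in 96-97% but the midway step in only about 5%, because that step is antisymmetric about the middle strength and has no quadratic component.

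**4. How the unit of analysis affects the trend test.** If the 120 recordings were pooled, the ratio of the slope's true variance to its nominal variance is about (1 + 1.4C^2)/(1 + L^2 + 0.117C^2), with 0.117 = 1.4/12.

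| L, C | Variance ratio | Pooled type I error (simulated) |
|---|---|---|
| 1, 0 | 1/2 = 0.50 | 0.9% |
| 2, 0 | 1/5 = 0.20 | 0.06% |
| 2, 1 | 2.4/5.117 = 0.47 | 1.4% |
| 1, 1 | 2.4/2.117 = 1.13 | 7.7% |
| 2, 2 | 6.6/5.467 = 1.21 | 10% |

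A one-sample t-test on the 10 subject slopes stays at 4.7-5.3% in all 25 settings tried.

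**The case against.** **The subject term could sit in an unseen statistical analysis plan.** This stands, and it makes that part secondary. Section 7.1 never says that recordings are pooled, so a reader who infers that the plan treats 120 recordings as independent goes beyond the text. Nor does the wording exclude a sound analysis: correlation coefficients in the plural, with regression, are compatible with one slope per subject followed by a group t-test. The direction of any pooling error is also unknown. For a truly linear 2 SD rise with L 1-2 and C up to 1, power is 97-100% pooled and 99-100% on subject slopes, so the verdict on trend would hardly change. None of this touches the mismatch between endpoint and test, because section 7.1 does state the test.

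**Not every non-linear response would pass.** Correct. A symmetric hump (0, 1, 2, 2, 1, 0 SD) gives a significant slope in 0.8-4.3% of trials pooled and about 5% on subject slopes. A regression on the six strength means flags the 2 SD plateau in only about 51%. So the claim that any non-linear response would be called significant under every reading fails. What remains is monotone shapes with a pooled or subject-level test.

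**It is a pilot without confirmatory decisions.** This lowers the weight of exact error rates. It does not excuse a test that answers a different question from the endpoint.

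**Interrupted stimuli.** Because "The stimulus is interrupted when the pain intensity exceeds 7", a reader might infer that strong-stimulus recordings are lost and the slope biased. The Protocol says the stimulus stops, not that the recording is discarded, and it gives no rate. No conclusion is drawn from it.

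**Conclusion.** The Protocol names linearity as an aim and a main endpoint, and the only stated test cannot establish it. That conclusion needs no assumption about variances. The illustration does: with L 1-2, C up to 1 and two-sided 0.05, a 2 SD plateau passes as a significant slope in 93-100% of trials, and a 2 SD midway step in nearly all. It applies to monotone non-linear shapes.

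The unit of analysis is a clarification to make at the same time, not a demonstrated error. Pooling, which the text permits but does not state, would give a type I error from below 0.1% to about 10% for L 1-2 and C no larger than L, against about 5% with subject slopes. This should be fixed, but it does not undermine the study.

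**What to change.** In section 7.1:

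1. Keep the slope as the test of trend, with the subject as unit: one slope per subject on the baseline series and a one-sample t-test on the 10 slopes (9 df). Report the mean slope with 95% CI and the between-subject slope SD. State baseline as a choice, since the present sentence does not restrict itself to one of the three sessions. Correlation coefficients can stay as description.
2. Add a test of departure from linearity: a within-subject lack-of-fit test with 4 df for the mean deviation from each subject's fitted line, against the subject-by-strength residual.
3. Show the mean response with 95% CI at each of the six strengths.

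The cost is about three sentences and no new data. There are two downsides. If all subjects share one level and slope, the subject-slope test has 80% power where pooling has 88%. And a non-significant lack-of-fit test in 10 subjects does not prove linearity: even the quadratic test, which is aimed at a bend of this kind, detects a 1 SD plateau in only about 50% of trials. The plotted means and intervals should therefore carry part of the conclusion.
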